If the NC is negative, i.e., the AKIRisk score is  $\leq 0.3 \text{ (ng/ml)}^2/1000$  (at first and second measurement, if applicable) or not assessable within the 2- to 6-hour window after T0, NC assessment may be repeated up to 4 times until 22 hours after T0. Urine sampling should be done at intervals of at least 1 hour. If all the NC assessments are negative up to 22 hours after T0, the subject cannot be randomized and will be followed up in the observational cohort (see below).

Randomized subjects will receive 3 subsequent treatments with ASP1128 or matching placebo, which will be applied intravenously through a peripheral/central catheter. The first administration of study drug will occur after randomization, as soon as possible after the positive NC. If NC is positive in the initial 2 to 6 hours post T0 period, the first dose of IP should be completed within 8 hours after T0. If NC is positive in any of the additional NC measurements within 22 hours after T0, the first dose should be completed as soon as possible but within 24 hours after T0.

In case of reoperation on the day of surgery (e.g., for immediate surgical complications like ongoing hemorrhage), the same time range for NC and drug administration applies in relation to T0 (i.e., NC between 2 and 22 hours and first investigational drug administration within 24 hours). A reoperation is no reason for not enrolling a subject as long as the NC can be performed at the described time points. If for any reason the AKIRisk score cannot be assessed within the 2 to 22 hours from T0, the subject cannot be randomized and will be a screen failure. If the subject is randomized, but for any reason the first administration of the study drug cannot be done within 24 hours after T0, the subject should not be withdrawn from the study as an intention-to-treat principle. The indication of reoperation will be recorded as an adverse event (AE) in the electronic case report form (eCRF) as well as the (reason for) missed drug administration.

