Study drug will need to be prepared for infusion by the study staff in the ICU. A detailed instruction is described in the pharmacy manual. The pH of the solution for injection is around 10 and there is a minor risk for irritation at the infusion site. Based on the results of the phase 1 study in healthy subjects it was determined that administration via a central line is allowed, but not required. The study drug can also be infused in a peripheral line on the forearm. The chosen peripheral line has to be reserved for study drug administration to avoid physicochemical interaction. If subjects have a central line this can be used for administration of study drug provided that 1 of the lumina is reserved for study drug in order to avoid physicochemical interactions.

After surgery, UO will be monitored, safety assessments will be done and laboratory tests (including NC, serum creatinine (SCr; cystatin-C and other biomarkers) will be performed as per the Schedule of Assessments [[Table 1](#)].

#### Visit 3, 4 and 5

It is expected that the subject will leave the ICU within 12 to 48 hours after surgery, but will remain in the hospital. Drug administration may be done via a central line in the ICU; however, this central line may have to be removed when the subject leaves the ICU. In this case, the study drug can also be infused in a peripheral line on the forearm. The chosen peripheral line has to be reserved for study drug administration to avoid physicochemical interaction. Please note that blood samples for pharmacokinetic measurements should be taken from a different location than the location of the peripheral intravenous device used for drug administration. A detailed instruction on drug preparation and administration is described in the pharmacy manual.

If the first dose of IP administration is completed within 8 hours after T0, the second dose of IP will be administered at 24 hours after T0 and the third dose of IP will be administered at 48 hours after T0. If the first dose of IP administration is completed past 8 hours after T0, the second dose of IP will be administered at 16 hours after the start of the first dose, and the third dose of IP will be administered at 40 hours after the start of the first dose of IP.

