16. Subject has surgery scheduled to correct major congenital heart defect.

17. Subject has current or previous malignant disease. Subjects with a history of cancer are considered eligible if the subject has undergone therapy and the subject has been considered disease free or progression free for at least 5 years. Subject with completely excised basal cell carcinoma or squamous cell carcinoma of the skin and completely excised cervical cancer in situ are also considered eligible.

*Preoperatively at the Day of Surgery:*

18. Exclusion criteria 1 to 17 are applicable at this time.
19. Subject has AKI (any stage) present at presurgery baseline at the discretion of the investigator.
20. Subject has known or suspected infection/sepsis at time of presurgery baseline at the discretion of investigator.

*Perioperative Exclusion Criteria:*

21. Subject requires Extracorporeal Membrane Oxygenation (ECMO) during or after completion of surgery.
22. Subject requires ventricular assist device (VAD) during or after completion of surgery.
23. Subject has surgery performed “Off-Pump” at any time during surgery.

*General:*

24. Subject has other condition, which, in the investigator’s opinion, makes the subject unsuitable for study participation.
25. Female subject who is pregnant or lactating or has a positive pregnancy test within 72 hours prior to screening and/or randomization, has been pregnant within 6 months before screening assessment or breastfeeding within 3 months before screening or who is planning to become pregnant within the total study period.
26. Subject has a known or suspected hypersensitivity to ASP1128 or any components of the formulation used.
27. Subject is an employee of the Astellas Group or the contract research organization (CRO) involved in the study.

Waivers to the inclusion and exclusion criteria will **NOT** be allowed.

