## **4 SAMPLE SIZE**

Sample size of this study is 220 randomized subjects (110 subjects in the ASP1128 group and 110 subjects in the placebo group).

The above sample size provides 80% power to detect the difference between ASP1128 and placebo on the primary endpoint of AKI proportion in the case of not considering an interim analysis, assuming the followings:

- AKI proportion in the placebo group is 60%
- Relative risk of ASP1128 against placebo is 0.7 (30% reduction)
- 1-sided significance level is 0.05
- Drop-out rate is around 10%

In addition, an interim analysis at 60% of enrollment as described below is planned by East® 6 software. Considering the interim analysis, the power is 78%.

- Futility stop criteria: conditional power to detect the relative difference between ASP1128 and placebo on the primary endpoint of AKI proportion is less than 10%, that is, 1-sided p-value is larger than 0.259, when approximately 60% of the planned acute kidney injury based on serum creatinine within 72 hours after Time point 0 (T0) (AKI-SCr72h) data have been collected in the study.
- There will be no provision to stop the study for efficacy in the interim analysis, so no efficacy stop criteria are defined.

Approximately 1000 subjects will be screened to enroll 600 subjects who meet the presurgery selection criteria. It is expected that 1 out of 3 subjects enrolled will meet the postsurgery criterion of having a NC AKIRisk score  $> 0.3 \text{ (ng/mL)}^2/1000$  and can be randomized: the

number of subjects to be randomized is 220. The subjects that have an AKIRisk score of  $\leq 0.3$  at the postsurgery 2- to 6-hour assessment will be enrolled in the observational cohort.

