### 6.1.2 Secondary Efficacy Endpoints

1. Proportion of subjects developing AKI (any stage) based on SCr criteria from the KDIGO guideline within 7 days after T0 (i.e., until Visit 8) (AKI-SCr7d).

[SCr evaluation visit: baseline, Visit 3, 4, 5, 6, 7 and 8 (24 hours, 48 hours, 72 hours after T0, and Day 5, 6 and 7/DoD). If the hospital discharge is earlier than Day 7, then the visits prior to DoD and Visit 8 (DoD) will be used.]

- If the subject meets at least one of the following conditions, then the subject will be treated as developing AKI-SCr7d.
  - Increasing in SCr  $\geq 0.3 \text{ mg/dL}$  within any 48 hours until Visit 8; and/or,
  - Increasing in SCr  $\geq 1.5$  times baseline until Visit 8.

2. Proportion of subjects developing AKI based on all captured criteria from the KDIGO guideline within 72 hours after T0 (AKI-KDIGO72h).

[SCr evaluation visit: baseline, Visit 3, 4 and 5 (24, 48, 72 hours after T0)]

[UO evaluation visit: Visit 3, 4, and 5 (0-12 hours, 12-24 hours, 0-24 hours, ..., and 48-60 hours, 60-72 hours and 48-72 hours after T0)]

- If the subject meets at least one of the following conditions, then the subject will be treated as developing AKI-KDIGO72h.
  - Increasing in SCr  $\geq 0.3$  mg/dL within any 48 hours until Visit 5;
  - Increasing in SCr  $\geq 1.5$  times baseline until Visit 5; and/or,
  - Urine volume  $< 0.5$  ml/kg per hour for any one of 12 consecutive hours until Visit 5 (i.e., 0-12 hours after T0, 12-24 hours after T0, ..., or 60-72 hours after T0).
- 3. Proportion of subjects developing AKI based on all criteria from the KDIGO guideline within 7 days after T0 (AKI-KDIGO7d).

[SCr evaluation visit: baseline, Visit 3, 4, 5, 6, 7 and 8(24 hours, 48 hours, 72 hours after T0, and Day 5, 6 and 7/DoD). If the hospital discharge is earlier than Day 7, then the visits prior to DoD and Visit 8 (DoD) will be used.]

[UO evaluation visit: Visit 3, 4, 5, 6, 7 and 8 (0-12 hours, 12-24 hours, 0-24 hours, ..., and 120-132 hours, 132-144 hours and 120-144 hours after T0). If the hospital discharge is earlier than Day 7, then the visits prior to DoD and Visit 8 (DoD) will be used.]

  - If the subject meets at least one of the following conditions, then the subject will be treated as developing AKI-KDIGO7d.
    - Increasing in SCr  $\geq 0.3$  mg/dL within any 48 hours until Visit 8;
    - Increasing in SCr  $\geq 1.5$  times baseline until Visit 8; and/or,

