  - At least one of eGFR based on cystatin-C equation within 7 days after T0  $\leq$  50% of the baseline value.

26. Proportion of subjects that have a reduction of NC AKIRisk score 24 hours after T0 (visit 3) to or below  $0.3 \text{ (ng/ml)}^2/1000$

27. Proportion of subjects with renal recovery, defined as a SCr value at hospital discharge equal to or lower than that at baseline

- SCr value at hospital discharge is defined as follows;

- If the hospital discharge is at or before day 7, the value at Visit 8 will be used.
- If the hospital discharge is after day 7, the value recorded as unscheduled event with check of “Last SCr value before hospital discharge.” will be used.

28. Time to ventilator weaning, defined as the time from T0 to extubation (i.e., removal of the endotracheal ventilation tube)

- Time to ventilator weaning is defined as: (Date and time of Extubation for the first record in “Mechanical Ventilation” form in eCRF – Date and time of T0) in hours.

29. Acute physiology and chronic health evaluation II (APACHE-II) up to day 4 (if the subject is on the ICU)

30. Number of readmissions to ICU

31. Number of readmissions to hospital

- All readmissions after initial hospitalization are included. Initial hospitalization is a hospitalization which includes the day of surgery
- If the date of admission of a hospitalization record is the same as the date of discharge of the previous record, then the two records will be combined into one record.

32. Changes from baseline in SCr, S-cystatin-C, eGFR based on SCr and Cystatin-C, and other biomarkers in blood and urine through 72 hours after T0

33. Area under the curve of SCr and S-cystatin-C through 72 hours after T0 (AUCSCr72h and AUCSCysC72h)

- AUCSCr72h is defined by Linear Trapezoidal Method as below;  
$$\text{AUCSCr72h (mg/dL*day)} = \text{sum of } (SCr_i + SCr_{i+1}) \times (Time_{i+1} - Time_i) / 2$$
where i=Visit 2 to 4
- AUCSCysC72h is defined in the same way as above.
- In the case of missing at 72 hours after T0, the missing value will be imputed from the last available value using Last Observation Carried Forward.

34. Area under the curve of SCr and S-cystatin-C through day 7 after T0(AUCSCr7d and AUCSCysC7d)

- AUCSCr7d and AUCSCysC7d are defined based on all available values through day 7 after T0 in the same way as AUCSCr72h and AUCSCysC72h

35. 5-level European Quality of Life 5 Dimensions Questionnaire (EQ-5D-5L) on baseline, visit 8, day 30 and day 90

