#### **7.4.2 Analysis of Secondary Endpoints**

[Analysis population: FAS, Analysis group: Randomization Arm]

- The secondary efficacy endpoints proportions (AKI-SCr7d, AKI-KDIGO72h, AKI-KDIGO7d, MAKE30 and MAKE90) will be analyzed using the stratified CMH test with strata to control for baseline eGFR based on Serum Creatinine (< 45 mL/min per 1.73 m^2, ≥ 45 mL/min per 1.73 m^2). The hypothesis testing will be performed at 2-sided 0.10 significance level. The MH estimate of the adjusted common risk ratio and 2-sided 90% confidence intervals will be calculated.
- As sensitivity analysis, chi-square test will be performed to evaluate the appropriateness of CMH test with strata to control for baseline eGFR based on Serum Creatinine (< 45 mL/min per 1.73 m^2, ≥ 45 mL/min per 1.73 m^2). The estimates of the risk ratio and 2-sided 90% confidence intervals will be calculated.
- Additional sensitivity analysis will be performed to evaluate the impact on the analysis of AKI/MAKE proportions due to any missing data/assessments and any loss to follow-up. If there is a missing value at any evaluation visit and the subject don't have the data meeting the criteria of the endpoint, then MI will be conducted for each missing component data firstly, then AKI/MAKE endpoint will be derived based on the imputed data.
- In additional, different definition of handling of missing data will be used. The subjects whose status of AKI/MAKE endpoint is unknown due to, say, the missing data of SCr will be counted as AKI/MAKE event. That is, if there is a missing value at any evaluation visit, then the subject will be counted as AKI/MAKE event. The same analysis as primary analysis (CMH test) by using this handling of missing data will be performed.
- As exploratory analyses, the association between MAKE30/MAKE90 (and also each individual outcomes, of all-cause mortality, initiation of RRT and eGFR based on SCr at day 30 (Visit 9)/day 90 (Visit 10) equal to or less than 75% of the baseline value) and primary, secondary and exploratory endpoint of AKI proportion is evaluated by a contingency table. The following endpoints of AKI proportion will be used:
  - AKI-SCr72h (primary endpoint),
  - AKI-SCr7d (secondary endpoint),
  - AKI-KDIGO72h (secondary endpoint),
  - AKI-KDIGO7d (secondary endpoint),
  - All stages AKI-UO (within 72 hours after T0)
  - All stages AKI-UO (within 7 days after T0),
  - AKI-UO stage 3 (within 72 hours after T0),

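### The AKI-KDIGO endpoints and time to ventilator weaning count events completed before randomisation, which pulls these secondary and exploratory estimates towards no effect

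*SAP*

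**What the plan says.** **Endpoint clock.** SAP 6.1.2 item 2 (AKI-KDIGO72h) makes a subject an event if urine volume is below 0.5 mL/kg per hour "for any one of 12 consecutive hours until Visit 5 (i.e., 0-12 hours after T0, 12-24 hours after T0" and so on in fixed 12 h blocks. Item 3 (AKI-KDIGO7d) and SAP 6.1.3 item 18 (AKI-KDIGO5d) also start with the 0-12 h block. Items 15, 16, 19 and 20 of SAP 6.1.3 use AKI-UO stages, whose stage 3 definition (SAP Table 3) includes anuria for over 12 h. SAP 6.1.3 item 28 reads "Time to ventilator weaning, defined as the time from T0 to extubation (i.e., removal of the endotracheal ventilation tube"), and SAP 7.4.4 analyses it by log-rank test and a Cox model with treatment only.

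**Randomisation clock.** Protocol 2.2.1 (version 2.0) allows repeat NephroCheck testing up to 22 h after T0. For subjects who turn positive on those repeats, "the first dose should be completed as soon as possible but within 24 hours after T0".

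**What might remove early events.** The only AKI exclusion concerns the time before surgery: "Subject has AKI (any stage) present at presurgery baseline at the discretion of the investigator" (Protocol 3.3, criterion 19). The full analysis set is everyone randomised and dosed. SAP Table 12 adds subgroups by first dose within or after T0 + 8 h, for the primary and secondary endpoints.

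**Testing.** For the secondary endpoints, "The hypothesis testing will be performed at 2-sided 0.10 significance level" (SAP 7.4.2).

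**The concern.** An event that is complete before assignment is a baseline fact that the drug cannot change. Counting it as an outcome adds the same expected share of events to both arms and moves the risk ratio or hazard ratio towards 1. Amendment 1 widened the NephroCheck window because a notable number of observational-cohort subjects turned positive after 6 h, so late randomisation is expected. The urine-output and weaning clocks nevertheless stayed at T0.

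The 0-12 h block may also carry more weight than its length suggests. Protocol 5.3.1.2 records 12-hourly urine output only in the ICU, and Protocol 2.2.1 says "It is expected that the subject will leave the ICU within 12 to 48 hours after surgery". Later 12 h blocks will therefore be captured less often. That is an inference from the schedule, not a stated fact.

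At stake are two secondary endpoints tested at 0.10 and several exploratory ones. In a proof-of-concept trial, muted supporting results can weigh on the decision to continue.

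**Working it through.** **1. The plan's own power figure.** SAP 4 gives 60% AKI on placebo, a relative risk of 0.7 (so 42% on ASP1128), 110 per arm, about 10% drop-out and "1-sided significance level is 0.05". It states: "The above sample size provides 80% power to detect the difference between ASP1128 and placebo". Evaluable subjects: 110 × 0.9 = 99 per arm. With mean proportion 0.51, the pooled two-proportion formula is

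Power = Φ{[0.18 − 1.645 √(2 × 0.51 × 0.49 / 99)] / √[(0.60 × 0.40 + 0.42 × 0.58) / 99]} = Φ(0.903) = 81.7%.

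This is within 2 points of the stated 80%. One-sided 0.05 has the same critical value as two-sided 0.10, so the formula also serves the secondary tests.

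**2. Which windows can close before randomisation.** The 0-12 h block closes first for anyone randomised after 12 h. The 12-24 h block, and the 24 h rule for stage 3, end no earlier than the 24 h limit on the first dose, so neither can be completed beforehand on schedule. A subject dosed within 8 h has no closed block. For weaning, any extubation before randomisation counts, on either route.

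**3. Attenuation of AKI-KDIGO.** Assumptions, none in the documents: AKI-KDIGO72h has the primary endpoint's 60% placebo rate in total, a share f of subjects have a pre-randomisation event, and the true risk ratio on later events is 0.70.

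Observed risk ratio = [f + 0.7(0.60 − f)] / 0.60.

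After removing the early events the risk ratio is 0.70. The remaining placebo rate depends on what those subjects do later:
- no later event in them: 0.60 − f
- later events independent of early ones: (0.60 − f)/(1 − f)

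| f | Observed RR | Power, plan's rule | Power after removal, no later event | Power after removal, independent |
|---|---|---|---|---|
| 5 points | 0.725 | 75.4% | 75.5% | 79% |
| 10 points | 0.75 | 68.2% | 69.0% | 76% |
| 20 points | 0.80 | 52.0% | 55.5% | 69% |

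The gain from removal is 0.1, 0.8 and 3.5 points in the first case and about 4, 8 and 17 in the second.

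**4. When the effect is small.** Alternatively, put the early events on top of 60% and 42%, independently. If 25% of subjects are randomised after 12 h and 10% of those are oliguric at 0-12 h, the share is 2.5 points. The rates become 0.60 + 0.40 × 0.025 = 0.61 and 0.42 + 0.58 × 0.025 = 0.4345. The risk ratio is 0.712 and power 80.0%, a loss of 1.7 points from 81.7%.

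**5. Weaning.** Assume a hazard ratio of 1.43 after randomisation, 198 extubations and a share g extubated before randomisation. Average log hazard ratio from T0 = (1 − g) × log 1.43; power = Φ(√(events/4) × log HR − 1.645).

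| g | HR from T0 | Power from T0 | Power, post-randomisation events only |
|---|---|---|---|
| 10% | 1.38 | 73% | 77% |
| 25% | 1.31 | 60% | 70% |
| 50% | 1.20 | 35% | 55% |
| 75% | 1.09 | 16% | 35% |

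A small simulation (300 runs per scenario, 15-64% extubated before randomisation) gave T0-based hazard ratios of 1.34 to 1.12, against 1.42 to 1.45 with delayed entry.

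**The case against.** The T0 clock is deliberate. Protocol 2.2.1 treats T0 as the start of the ischaemia-reperfusion state, and the endpoints are defined relative to it. A randomisation-based rule also gives subjects unequal numbers of counted windows: 72/12 = 6 blocks, or 5 if randomised after 12 h. Both points stand. They are reasons to keep the T0 definition and put a second analysis beside it.

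The first-dose subgroups in SAP Table 12 partly help, since the within-8-h subgroup has no closed block. But they are unadjusted, leave the closed block in the late subgroup, and do not cover weaning or the exploratory AKI-UO endpoints.

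A reader might infer more than the documents support:
- **That the trial's validity or primary result is damaged.** Randomisation balances these events, so the tests keep their level. AKI-SCr72h uses creatinine only and is untouched by this mechanism.
- **That the fix recovers the whole gap to 82% power.** That requires every early-oliguric subject to be a later placebo event as well. Removing early events normally lowers the event count too. Overlap beyond independence would raise the gain above the last column in step 3, but the documents say nothing about it.
- **That closed windows or early extubations will be common.** If late samples were uniform over 6-22 h, (22 − 12)/(22 − 6) = 63% would fall after 12 h, but that timing is undocumented, and repeats soon after 6 h would lower it. Even with half of all subjects on the late route, 5 points needs oliguria in 5/(50 × 0.625) = 16% of those sampled after 12 h, and 20 points needs 64%. With a quarter on the late route, 20 points would need 128%, which is impossible. ICU exit times are not extubation times, and the documents give none.

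**Conclusion.** The concern holds as attenuation of secondary and exploratory estimates. The plan's rules count 0-12 h oliguria, including anuria over 12 h, for subjects randomised after 12 h, and count extubations before randomisation, with no provision to remove either. The direction is towards a risk ratio or hazard ratio of 1.

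The size cannot be derived. It depends on the share randomised after 12 h, their 0-12 h oliguria rate and the extubation times, none of which is given. On the assumptions in step 3, the observed risk ratio is 0.73 to 0.80 instead of 0.70, and the power recoverable ranges from almost nothing to about 17 points. If 2.5 points of subjects or fewer are affected, the loss is under 2 points of power. The case for acting is that the change is cheap, not that the loss is known to be large.

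**What to change.** In SAP 6.1.2 items 2-3, and in the urine-output parts of SAP 6.1.3 items 15, 16 and 18-20, add a prespecified analysis that ignores, in both arms, any urine-output window ending before the subject's randomisation time. Report the number of pre-randomisation events by arm next to the T0-based result. Leave the creatinine and cystatin-C components as they are.

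For SAP 6.1.3 item 28, use delayed entry at randomisation, so that only subjects still intubated then contribute, and keep the T0 version alongside. Both rules depend only on facts fixed before assignment, so they introduce no post-randomisation selection.

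The cost is SAP wording and derivation code. T0 and extubation times are recorded. Randomisation goes through the IRT, so its time should be obtainable, though the documents do not list it as an analysis variable. The downsides are unequal numbers of counted windows between subjects and fewer subjects in the weaning analysis.
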